## **17.0 DATA AND SAFETY MONITORING (Interim monitoring)**

The Research Team will continuously monitor study accruals, toxicities, and response to treatment. The UM/Sylvester Comprehensive Cancer Center's Data and Safety Monitoring Committee (DSMC) will monitor this protocol according to the Cancer Center's DSM Plan. In its oversight capacity, the DSMC bears responsibility for suspending or terminating this study. DSMC oversight of the conduct of this trial includes ongoing review of accrual and adverse event data, and periodic review of response. The DSMC also reviews reports from internal audits of protocol compliance and data integrity conducted by the University of Miami, Office of Research Compliance Assessment. The guidelines appearing in this section are offered for DSMC consideration in assessing adverse events and response to study treatment.

### Early stopping guidelines

We propose the following guidelines for the DSMC in its review of accumulating data on toxicity and response. The proposed guidelines were developed using Bayesian methods, which can be applied at any stage of enrollment without advance specification of the number of interim analyses to be performed, or the number of patients evaluable for toxicity, or response, at the time such assessments are made (45, 46).

Under the Bayesian method, we assign a prior probability (level of belief at the start of the trial) to a range of possible values for the true toxicity rate, and likewise for the true response rate. As data on treated patients become available, each of these probability distributions is revised and the resulting posterior probability becomes the basis for recommending either early termination or continuation of the study.

Early stopping rule is applied to 30 patients who receive concurrent axitinib with pembrolizumab. Details are given in the remainder of this section.

### Early stopping due to safety

If a treatment-related (possible, probable, or definite) death occurs, enrollment will be suspended and continuation of the study will be reassessed by the DSMC.

If four out of first five treated patients experiences DLT then the study will be suspended and reviewed with the Data Safety Monitoring Committee for consideration of modification or

termination. It is based on Bayesian stopping rule that DLT rate should not exceed 40% with a posterior probability of 90% or higher.

For purposes of safety monitoring, we define an unacceptable toxicity to be any treatment-related DLT, where acute refers to the period of time from start of study treatment to one month following completion or discontinuation of treatment. Unacceptable toxicity is expected to occur in no more than 30% of study patients. Early stopping (suspension and possibly termination) will be considered if there is evidence that the proportion of patients experiencing unacceptable toxicity exceeds 40%. Specifically, we suggest as a guideline for early termination a posterior probability of 90% or higher that the rate of unacceptable toxicity exceeds 40%.

The table below shows specific instances where this guideline is met, thus suggesting early termination due to evidence of excessive toxicity.

Number of patients with DLT among 30 patients	Total patients evaluated	Observed toxicity rate
4	4 to 5	≥ 80%
5	6 to 7	≥ 71%
6	8 to 9	≥ 67%
7	10 to 11	≥ 64%
8	12 to 13	≥ 62%
9	14 to 15	≥ 60%
10	16 to 17	≥ 58%
11	18 to 19	≥ 57%
12	20 to 21	≥ 54%
13	22 to 24	≥ 54%
14	25 to 26	≥ 54%
15	27 to 28	≥ 53%
16	29	≥ 55%

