#### **16.4 Patient Enrollment and Sample Size**

The study will be conducted at Sylvester Comprehensive Cancer Center. Our expectation is that proposed treatment will improve PFS at 3 months from 19% to 40%. Assuming 15 months for enrollment and 12 months minimum follow-up, 40 evaluable patients (including expansion) will provide 97.5% power to reject 3 month PFS rate of 19% in favor of 3 month PFS rate of 40% using a one-sample survival test with one-sided 5% significance level using STPLAN (MD Anderson Biostatistics software) [6]. With estimated accrual of 1 patient every 2 months in the expansion cohort, we anticipate 18-24 months for patient enrollment followed by an additional year of follow up time. Expected time to study completion is 3 years from date open to enrollment.

For the secondary objectives utilizing patient samples, we anticipate that we will be able to obtain complete sets or measurements for all patients (pre-treatment, on-treatment, and post-treatment) to permit analysis of inpatient pharmacodynamic effect of therapy. However, a critical component of this study is the analysis for exploratory endpoints, which are hypothesis-generating in regards to potential biomarkers for response in sarcoma patients treated with concurrent axitinib/pembrolizumab. Thus, if our primary endpoint is met by the conclusion of enrollment and the combination appears active with potential benefit to patients, yet collection of tumor biopsies and peripheral blood sample collection was incomplete, we would consider extending enrollment to an additional 10 patients in an effort to obtain complete paired samples at the baseline, cycle 3, and off-study timepoints in responders and non-responders.

Power considerations for correlative studies: If we estimate 75% collection of complete, interpretable biopsies and blood samples from 40 patients, our analysis set of responders vs. non-responders will include approximately 10 responding patients and 20 non-responding patients. A sample size of 10 in the responder group and 20 in the non-responder group will provide 89.4% statistical power to detect a difference in mean change of 2.5 with a standard deviation of 1 at both time points, and a correlation between two measurement pairs of 0.2. The significance level is 0.00083 using Bonferroni adjustment ( $=0.05/60$ ).

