**Table 13. Stopping Rule for Safety**

For example, if 7 patients have been assessed for toxicity, the second row of the above table indicates that early stopping should be considered if 5 (71%) of these patients have experienced DLT.

Posterior probabilities used to derive the preceding table are calculated under a prior beta distribution with parameters  $\beta_1 = 0.6$  and  $\beta_2 = 1.4$ , which corresponds to an expected rate of 30% based on very limited information, roughly equivalent to having studied two patients. This prior distribution implies also an a priori chance of only 32% that the rate of unacceptable toxicity is 40% or greater.

Early stopping due to lack of efficacy

We do not propose early stopping of this trial based on interim assessment of efficacy. We need to gather preliminary evidence of efficacy of the treatment for this study population.

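### The safety stopping table departs from its own 90% posterior rule in small ways up to 29 patients and was not extended when the plan grew to 40 evaluable patients

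*Combined protocol and SAP*

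**What the plan says.** Section 17.0, under early stopping due to safety, gives the guideline in words: "we suggest as a guideline for early termination a posterior probability of 90% or higher that the rate of unacceptable toxicity exceeds 40" percent. Table 13 follows, introduced by "The table below shows specific instances where this guideline is met, thus suggesting early termination due to evidence of excessive toxicity". Below it the plan states how the table was made: "Posterior probabilities used to derive the preceding table are calculated under a prior beta distribution with parameters" 0.6 and 1.4, "which corresponds to an expected rate of 30% based on very limited information, roughly equivalent to having studied two patients". It adds a check figure: "This prior distribution implies also an a priori chance of only 32% that the rate of unacceptable toxicity is 40% or greater".

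The table runs from 4 DLTs in 4 to 5 patients to 16 DLTs in 29. Its first column is headed "Number of patients with DLT among 30 patients". The introduction to the stopping guidelines sets the scope: "Early stopping rule is applied to 30 patients who receive concurrent axitinib with pembrolizumab". The same introduction says that the Bayesian method may be used at any point in enrolment, and it gives no minimum number of patients.

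Section 16.4 bases the power statement on "40 evaluable patients (including expansion" cohort). The synopsis and Section 1.5 describe that cohort as up to 10 further patients with ASPS, added after the first 30 had been accrued.

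**The concern.** A table derived from a stated prior and cut-off should agree with them row by row. A committee member will read the table rather than compute beta tail areas. If a row disagrees with the rule in the text, the committee has two answers at that sample size and nothing says which governs.

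The larger issue is scope. The sample size in Section 16.4 was revised for the expansion, but the stopping rule in Section 17.0 still describes a 30-patient trial. One stated purpose of the expansion, in Section 1.5, is further safety data. Yet its patients fall outside the only quantitative DLT guideline in the plan, and no reason is given.

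**Working it through.** **Inputs, all from Section 17.0 unless noted.** Prior Beta(0.6, 1.4); threshold rate 0.40; cut-off 0.90; printed rows for n = 4 to 29. Planned evaluable patients: 40 (Section 16.4).

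**Formula.** With x DLTs in n patients the posterior is Beta(0.6 + x, 1.4 + n − x), and the guideline is met when

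P(rate > 0.40 | x, n) = 1 − F(0.40; 0.6 + x, 1.4 + n − x) ≥ 0.90.

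The boundary at each n is the smallest x that satisfies this.

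**Reproducing the plan's own figures first.** The prior mean is 0.6/(0.6 + 1.4) = 0.30, as stated. The prior probability of a rate above 0.40 is 0.3196, which matches the stated 32%. The lead-in rule of 4/5 gives 0.920, and the worked example of 5/7 gives 0.913. The printed boundary is the smallest qualifying x at 25 of the 26 values of n from 4 to 29. Five other priors were tried (Beta(0.8, 1.2), (1, 1), (0.3, 0.7), (1.2, 2.8) and (0.5, 0.5)); each moves other boundaries away from the printed table. The stated inputs are therefore the ones that were used.

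**Where the table departs.**

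| Point | Printed | Recomputed |
|---|---|---|
| n = 24 | 13 DLTs | 13/24: 0.896, not met; 14/24: 0.952, met |
| n = 20 to 21, rate | at least 54% | 12/20 = 60.0%; 12/21 = 57.1% (count of 12 correct: 0.923) |
| n = 3 | no row | 3/3: 0.936, met (2/2: 0.854, not met) |
| n = 30 to 40 | no rows | 16/30: 0.911, rising to 21/40: 0.932 |

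Three other printed rates are truncated although the rest are rounded: 10/17 = 58.8% is shown as 58%, 11/19 = 57.9% as 57%, and 15/28 = 53.6% as 53%.

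The n = 24 entry looks like rounding. The value 0.8962 becomes 0.90 at two decimals, while the highest posterior at one DLT below any printed boundary is 0.8906 (12/22), which becomes 0.89. A cut-off applied to two-decimal values would reproduce all 26 printed boundaries.

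**Operating effect.** Assume independent DLTs at a constant true rate, a look after every patient, and the boundary treated as binding. The distribution of the DLT count is carried forward one patient at a time, and the probability at or above the boundary is removed at each n.

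| True DLT rate | Printed table, to n=29 | Corrected (3/3 added, 14 at n=24), to n=29 | Corrected, to n=40 |
|---|---|---|---|
| 30% | 6.9% | 7.9% | 8.1% |
| 40% | 26.0% | 27.0% | 30.0% |
| 50% | 60.2% | 60.5% | 68.9% |
| 60% | 89.0% | 89.0% | 94.8% |

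At a true rate of 50%, among trials that have not reached the boundary by n=29, the extended rule would be reached in (68.9 − 60.5)/(100 − 60.5) = 8.4/39.5, or about 21%.

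**The case against.** The strongest reply is that little of this changes what the committee would do. Section 17.0 offers the rule as guidance for the DSMC's consideration, so nothing in the table stops the trial by itself. The table claims only to give specific instances, so leaving out 3/3 is an omission and not a wrong row, and the rule in words can be applied at n=3. The miss at 13/24 is 0.4 percentage points and errs towards earlier review. The 54% is in a display column and the count beside it is correct. All of this stands, and it is why the first three items are minor.

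A reader might take the chance of seeing 3/3 (0.5³ = 12.5% at a true rate of 50%, 0.6³ = 21.6% at 60%) as the effect of omitting that row. It is not. After 3/3 the printed table is reached by patient 5 if either of the next two patients has a DLT. The cases still unstopped at n=5 are p³(1 − p)²: 3.1% at 50% and 3.5% at 60%. Section 7.0 also allows axitinib titration only if 2 or fewer of the first five patients have a DLT, so 3/3 already blocks titration, although it does not suspend the study.

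On scope, the text and the column heading both say 30 openly. Ending at n=29 is consistent with that, since a boundary at n=30 could not halt enrolment in a 30-patient trial. A reader might infer an arithmetic error, or that expansion patients have no safety oversight. The documents support neither. Section 17.0 keeps continuous monitoring by the research team, ongoing DSMC review of adverse events, and suspension after a treatment-related death with no patient limit attached. What the reply does not answer is why a DLT guideline thought necessary for the first 30 patients lapses for the next 10.

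**Conclusion.** The point holds, with unequal weight across its parts. Up to n=29 the table has one boundary that fails the literal rule (13/24, probably rounding), one wrong printed rate (12/21), and one unlisted qualifying case (3/3). Correcting the two boundaries moves the stopping probability by about 1 point or less at true DLT rates from 30% to 60%. It would be wrong to infer that the table as a whole is unreliable or was built on another prior.

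The substantive part is that the 30-patient scope was not updated for the 40 evaluable patients now planned. This is a gap in scope, not in arithmetic. At a true DLT rate of 50% it is the difference between about 60% and about 69% in the chance of reaching the boundary. At the expected rate of 30%, carrying the corrected rule from n=29 to n=40 adds only 0.2 points (7.9% to 8.1%).

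These probabilities are counted from the first patient and assume a look after each one, which the plan permits but does not require. They are not conditional on the DLTs actually seen in the first 30 patients, which the documents do not report.

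**What to change.** Recompute Table 13 from the stated prior and cut-off. Under the literal rule the 13-DLT row covers n = 22 to 23 and the 14-DLT row covers n = 24 to 26. If the cut-off was meant to apply to a posterior rounded to two decimals, say so instead. Correct the 12-DLT rate to 57% and round every rate the same way. Either list 3/3 or state the number of patients at which the guideline starts.

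Reconcile the 30-patient scope in the Section 17.0 text and the table heading with the 40 evaluable patients in Section 16.4. If the sponsor and the DSMC keep the same rule for the expansion, the boundaries are:

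| Patients evaluated | DLTs |
|---|---|
| 29 to 30 | 16 |
| 31 to 32 | 17 |
| 33 to 34 | 18 |
| 35 to 37 | 19 |
| 38 to 39 | 20 |
| 40 | 21 |

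If they decide that the DLT guideline should end at 30, the plan should say so, give the reason, and name what monitoring applies afterwards. The cost is one recomputed table, its heading and a sentence or two of text. No new data are needed.

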**Table 13. Stopping Rule for Safety**

For example, if 7 patients have been assessed for toxicity, the second row of the above table indicates that early stopping should be considered if 5 (71%) of these patients have experienced DLT.

Posterior probabilities used to derive the preceding table are calculated under a prior beta distribution with parameters  $\beta_1 = 0.6$  and  $\beta_2 = 1.4$ , which corresponds to an expected rate of 30% based on very limited information, roughly equivalent to having studied two patients. This prior distribution implies also an a priori chance of only 32% that the rate of unacceptable toxicity is 40% or greater.

Early stopping due to lack of efficacy

We do not propose early stopping of this trial based on interim assessment of efficacy. We need to gather preliminary evidence of efficacy of the treatment for this study population.

## 18.0 DATA REPORTING

Data must be submitted according to the protocol requirements for all patients registered. Patients for whom documentation is inadequate to determine eligibility will generally be deemed ineligible.

## 19.0 STUDY MONITORING

This study will be monitored and/or audited (as applicable) according to the University of Miami requirements. See also <http://uresearch.miami.edu/regulatory-compliance-services/rcqa> and <http://research.med.miami.edu/clinical-research/crors>.

## 20.0 INVESTIGATOR RESPONSIBILITIES

### 20.1 Investigator Responsibility/Performance

The investigator will ensure that this study is conducted in accordance with all regulations governing the protection of human subjects. The investigator will ensure that all work and services described in or associated with this protocol will be conducted in accordance with the investigational plan, applicable regulations, and the highest standards of medical and clinical research practice.

### 20.2 Confidentiality

The investigator must ensure that each subject's anonymity will be maintained and each subject's identity will be protected from unauthorized parties. A number will be assigned to each subject upon study entry and the number and the subject's initials will be used to identify the subject for the duration of the study. The investigator will maintain all documents related to this study in strict confidence.

### 20.3 Informed Consent and Permission to Use Protected Health Information

It is the responsibility of the investigator to obtain written informed consent from each subject participating in this study after adequate explanation, in lay language, of the methods, objectives, anticipated benefits, and potential hazards of the study. The investigator must also explain that the subject is completely free to refuse to enter the study or to discontinue participation at any time (for any reason) and receive alternative conventional therapy as indicated. Prior to study participation, each subject will sign an IRB approved informed consent form and receive a copy of same (and information leaflet, if appropriate). For subjects not qualified or able to give legal consent, consent must be obtained from a parent, legal guardian, or custodian. The investigator or designee **must** explain to the subject before enrollment into the study that for evaluation of study results, the subject's protected health information obtained during

the study may be shared with the study sponsor, regulatory agencies, and the IRB. It is the investigator's (or designee's) responsibility to obtain permission to use protected health information per HIPAA from each subject, or if appropriate, the subjects' parent or legal guardian.

#### **20.4 Source Documentation and Investigator Files**

The investigator must maintain adequate and accurate records to fully document the conduct of the study and to ensure that study data can be subsequently verified. These documents should be classified into two separate categories: (1) investigator study file and (2) subject clinical source documents that corroborate data collected on the CRF's. Subject clinical source documents may include hospital/clinic patient records; physician's and nurse's notes; appointment book; original laboratory, ECG, EEG, radiology, pathology, and special assessment reports; pharmacy dispensing records; subject diaries; signed informed consent forms; and consultant letters. When the CRF or any form is used as the source document, this must be clearly stated in the investigator study file. Minimally, the following be documented in source documents:

- Medical history/physical condition and diagnosis of the subject before involvement in the study sufficient to verify protocol entry criteria
- Study number, assigned subject number, and verification that written informed consent was obtained (each recorded in dated and signed notes on the day of entry into the study)
- Progress notes for each subject visit
- Documentation of treatment
- Laboratory test results
- Adverse events (action taken and resolution)
- Condition and response of subject upon completion of or early termination from the study

#### **20.5 Recording and Processing of Data**

If using hard copies of CRF's, study center personnel will complete individual CRF's in black ink. All corrections to entered data will be made by drawing a single line through the information to be corrected without obscuring it. All corrections will be initialed, dated and explained, if necessary. The use of "white-out" or obscuring correction tape will be prohibited. A CRF is required for every patient who received any amount of study treatment. The investigator will ensure that the CRF's are accurate, complete, legible and timely. Separate source records are required to support all CRF entries except those for which use of the CRF as source document is clearly allowed per note in the investigator study file.

Data must be submitted according to the protocol requirements for ALL patients registered. Patients for whom documentation is inadequate to determine eligibility will generally be deemed ineligible.

A list of forms to be submitted, as well as expectation dates may be found in Appendix B.

#### **20.6 Non-Protocol Research**

No investigative procedures other than those described in this protocol will be undertaken on the enrolled subjects without the agreement of the IRB.

#### **20.7 Ethics**

The investigator agrees to conduct the study in compliance with the protocol, current good clinical practices, and all applicable (local, FDA) regulatory guidelines and standard of ethics.

UM Ethics Programs' Research Ethics Consultation Service (RECS) is a free resource for UM Researchers. See the website for further information:

<http://www.miami.edu/index.php/ethics/projects/recs/>

#### **20.8 Essential documents for the conduct of a clinical trial**

Essential documents are those documents with individually and collectively permit evaluation of the conduct of a trial and the quality of the data produced. The following documents should be on file: 1) 1572 or investigator's agreement (for studies involving IND drugs or devices, respectively); 2) CV's and license of all Investigators; 3) IRB documentation/correspondance and 4) Documentation of IRB certification

## **APPENDIX A: EXPEDITED ADVERSE EVENT (AE) REPORTING REQUIREMENTS**

For all AEs that meet criteria for expedited reporting, the Principal Investigator (PI) is obligated to pursue and provide follow-up reporting information until the event has resolved or until an acceptable medical endpoint has been reached (i.e. for the duration specified in the protocol), or the patient is lost to follow-up.

The PI and all applicable research study team members should become familiar with the safety profile of the investigational agent(s) and/or intervention at the start of the study and for the duration of the research, e.g. by reviewing the Investigator's Brochure (IB) and any Safety Reports released, by the Sponsor as applicable.

### **I. FDA Expedited Reporting**

- a. Sponsor-Investigators i.e. IND Holders, have additional reporting requirements to the FDA and other committees, and should consult the applicable regulations and agency guidelines for these requirements.
- b. Since this protocol involves the use of FDA IND agent(s), completion of the FDA MedWatch 3500A Reporting Form is required for Sponsor-Investigators. The Form can be obtained electronically at:  
<http://www.fda.gov/downloads/AboutFDA/ReportsManualsForms/Forms/UCM048334.pdf>
  - i. All serious, unexpected (unanticipated) and suspected adverse events must be directly reported to the FDA within 15 calendar days of being made known to the Principal Investigator (PI).
  - ii. All fatal or life-threatening AEs must be directly reported to the FDA within 7 calendar days of being made known to the PI.
- c. For more information regarding reporting to the FDA, please refer to the FDA website for REPORTING GUIDELINES:  
<http://www.fda.gov/Safety/MedWatch/HowToReport/default.htm>

